8. RESEARCH QUESTION AND OBJECTIVES

The study objectives are to:

1. Describe the use of gabapentin in pregnancy.
2. Estimate the risk of major congenital malformations, other birth outcomes, and selected postnatal neurodevelopmental outcomes of pregnancies with exposure to gabapentin as compared with pregnancies with: no exposure to antiepileptic drugs (AEDs); exposure to pregabalin; exposure to lamotrigine; exposure to pregabalin or lamotrigine.

The primary objectives of the study are to:

- Describe use of gabapentin, pregabalin, and lamotrigine during pregnancy overall (for any therapeutic use), and by:
 - trimester of pregnancy,
 - indication,
 - cumulative dose,
 - calendar year of delivery;

Description of exposure will be performed for all pregnancies, including pregnancies with monotherapy exposure (defined as no concomitant administration with other AEDs) and pregnancies with polytherapy exposure (defined as concomitant administration with other AEDs), as well as the subset of only pregnancies with monotherapy exposure.

- Calculate the prevalence of major congenital malformations in pregnancies with first-trimester exposure to:
 - gabapentin;
 - pregabalin;
 - lamotrigine;
 - pregabalin or lamotrigine.
- Perform a sensitivity analysis to calculate the prevalence of major congenital malformations that includes stillbirth and pregnancies ending in therapeutic 2nd trimester induced abortion in the definition of prevalence in pregnancies with first-trimester exposure to:
 - gabapentin;
 - pregabalin;
 - lamotrigine;
 - pregabalin or lamotrigine.
- Estimate the associations between first-trimester exposure to gabapentin and prevalence of major congenital malformations, as compared with:
 - no exposure to AEDs during the first trimester;
 - exposure to pregabalin during the first trimester;
 - exposure to lamotrigine during the first trimester;
 - exposure to pregabalin or lamotrigine during the first trimester.
- Calculate the prevalence of pre-specified birth outcomes including stillbirth, low birth weight, small for gestational age (SGA), preterm birth, low Apgar score, microcephaly, among pregnancies with any trimester exposure to:
 - gabapentin;
 - pregabalin;
 - lamotrigine;
 - pregabalin or lamotrigine.
- Estimate the associations between exposure to gabapentin any time during pregnancy and other pre-specified birth outcomes, including stillbirth, low birth weight, small for gestational age (SGA), preterm birth, low Apgar score, microcephaly, as compared with:
 - no exposure to AEDs any time during pregnancy;
 - exposure to pregabalin any time during pregnancy;
 - exposure to lamotrigine any time during pregnancy;
 - exposure to pregabalin or lamotrigine any time during pregnancy.

The secondary objectives of the study are to:

- Calculate the incidence rates of pre-specified postnatal neurodevelopmental outcomes (attention-deficit hyperactivity disorders, pervasive developmental disorders, learning disorders and intellectual disabilities) with any trimester exposure to:
 - gabapentin;
 - pregabalin;
 - lamotrigine;
 - pregabalin or lamotrigine.
- Estimate the associations between exposure to gabapentin any time during pregnancy and the pre-specified postnatal neurodevelopmental outcomes, as compared with:
 - no exposure to AEDs any time during pregnancy;
 - exposure to pregabalin any time during pregnancy;
 - exposure to lamotrigine any time during pregnancy;
 - exposure to pregabalin or lamotrigine any time during pregnancy.

The calculations of ‘prevalence’ and ‘incidence rate’ are further described in [section 9.7.1](#) and [section 9.7.2](#) respectively. All prevalence and incidence rate calculations will be determined for all pregnancies, including pregnancies with monotherapy exposure and pregnancies with polytherapy exposure, as well as the subset of only pregnancies with monotherapy exposure. The prevalence of major congenital malformations does not include stillbirth and pregnancies ending in therapeutic 2nd trimester induced abortion, unless otherwise specified in sensitivity analyses (see [section 9.7.6.](#)).

9. RESEARCH METHODS

9.1. Study design, study period, and follow-up

This PASS is a population-based study and is based on routinely collected data from national administrative and medical registers in four Nordic countries. All births from 1 January 2005 to 31 December 2015 in Denmark, Finland, and Norway, and during 1 July 2006 to 31 December 2016 in Sweden will be included. Follow-up for the postnatal neurodevelopmental outcomes, when available, will be a minimum of 1 year postnatally and for the maximum period available in the dataset for each birth ([Table 1](#)). However, for a variety reasons, either related to the individual or to the family (e.g. emigration, death), follow-up could be infeasible in individual cases. Each country has tax-supported universal health care;⁸ routine and prospectively collected data on outpatient dispensings, live and still births, hospital diagnoses, migrations and deaths; and individual-level data linkage including exact mother-child linkage (mother’s personal identifier is a data field in the child’s birth record).

Because indication may be related to the occurrence of the study outcomes, medications used to treat the same indications as gabapentin (epilepsy and neuropathic pain) are selected as comparators to control for potential confounding.

The birth outcomes chosen are standard outcomes used to evaluate the safety of prenatal medication exposure for offspring and have been examined in previous studies of medication safety in pregnancy.^{4-6,8,10,12}

9.2. Setting

[figure not shown]
This study will be conducted using data from four Nordic countries: Denmark, Finland, Norway, and Sweden.⁸ All live births and stillbirths are recorded in birth registries (in all countries except Sweden from gestational week 22 from July 2008 onwards; in Sweden, from gestational week 28 from July 2008 onwards). During the study period, there were approximately 580,000 – 730,000 live births in each of Denmark, Finland, and Norway, and 1,100,000 in Sweden.⁹ The start of the study period in each country was selected to ensure availability of gabapentin and the comparators on the market and availability of data on outpatient dispensings for at least 12 months before the end of the earliest identified pregnancy. For example, pregnancy ending at term with a live birth on 1 January 2005 in Denmark will have prescription history from 1 January 2004, thus covering the 9 months of gestation and 3 months preconception.

Population-based healthcare registries in Nordic countries are an optimal setting for examining safety of medicines in pregnancy. Their most important strengths are capture of all births and, clinically relevant birth and postnatal outcomes for this study; last menstrual period (LMP), depending on country is either directly recorded in the birth registry or estimated from gestational age; routine capture of dispensings of prescription medications to pregnant women; extensive information about maternal and offspring demographic information; and exact linkage between the maternal and the offspring record.

Study population

The study population will consist of all births identified in the respective registries from 1 January 2005 to 31 December 2015 in Denmark, Finland, and Norway and all births identified from 1 July 2006 to 31 December 2016 in Sweden, [Figure 1](#) .

Figure 1. Study population flow diagram

As all birth outcomes will have occurred as of the date of delivery, prevalence will be used as a measure of outcome occurrence.¹⁰ To allow for delayed reporting/diagnosis, all congenital malformations diagnosis recorded within one year of age will be included, according to the standard procedure used by the European Network of Congenital Anomaly Registers (EUROCAT)¹¹ through the end of 2016 in Denmark, Finland and Norway and through the end of 2017 in Sweden. In addition, available information on pregnancies ending in 2nd trimester therapeutic induced abortions will be identified in Denmark, Finland and Norway. Information on pregnancies ending in 2nd trimester therapeutic induced abortions is not available from Sweden for the specific study period. It will be especially important to identify pregnancy terminations due to malformations of the nervous system, as nearly half of the pregnancies affected by nervous system malformations may be terminated.¹²

Major congenital malformations and stillbirth prevalence will be described and compared using live and stillbirths as the denominator. For the birth outcomes other than major congenital malformations or stillbirth, prevalences at birth will be described and compared using live births as the denominator.

For the postnatal neurodevelopmental outcomes, livebirths of all gabapentin-exposed and the comparator pregnancies will be followed from the date of birth until the earliest record of a given outcome of interest, emigration (except Sweden and Norway, where emigration data are unavailable), death, or end of study (31 December 2016 in Denmark, Finland, and Norway; 31 December 2017 in Sweden); for this analysis, children in Norway born before 2008 will be excluded as the Patient Registry of Norway was launched in 2008. Thus, for the neurodevelopmental postnatal outcomes, livebirths will be followed up to a minimum of 1 year and a maximum of 8 years in Norway, 10 years postnatally in Denmark, and Finland, and up to a maximum 11.5 years postnatally in Sweden (Figure 2).

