9.2.1. Inclusion criteria

All births from 1 January 2005 through 31 December 2015 (both dates inclusive) in Denmark, Finland, and Norway and all births identified from 1 July 2006 through 31 December 2016 (both dates inclusive) in Sweden.

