9.3.2.1. Primary Outcomes (Birth outcomes)

- Major congenital malformations, any and specific malformation type, according to the EUROCAT classification¹⁴
- Stillbirth, as recorded in each country's birth registry
- Low birth weight (birth weight < 2500 g)
- Small for gestational age (SGA), defined, for singleton pregnancies, as a dichotomous variable (yes/no) of birth weight below 2 standard deviations (SDs) of sex- and gestational week specific distributions, using country-specific reference standard.^{13,15} SGA non-singleton gestations will be defined if appropriate reference standard can be defined/identified; otherwise set to missing.
- Preterm birth, defined as gestational age <37 weeks
- Low Apgar score at 5 minutes, defined as a dichotomous variable (score 0-6 vs. score 7-10)
- Microcephaly, defined as a dichotomous variable (yes/no) of head circumference at birth (cm) smaller than 2 SD of sex- and gestational week specific distribution, using country-specific reference standard

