9.7.7. Combining results

Crude and adjusted estimates of association from Sweden, Norway, and Finland will be transferred to Aarhus University, Aarhus, Denmark for meta-analyses or other combined analyses. Because of the similarities between the healthcare systems in the Nordic countries and the use of a common study protocol with well-defined selection of exposures, outcomes and covariates, a fixed-effects meta-analysis is justifiable applied.⁵⁵ Country-specific crude and adjusted estimates of association for each prespecified comparison will first be calculated and presented. These results will then be combined in a meta-analysis, or, if deemed more suitable, another method that allows incorporation into combined estimates of associations with no exposed events, such as Mantel-Haenszel pooling methods.⁵⁶ For each outcome the coordinating centre will use the inverse variance method in the fixed effects meta-analyses, which is weighting the country-specific estimates of association by the inverse of the within-country variances. Homogeneity of the estimates will be verified, and a random-effects meta-analysis will be considered as an alternative should the estimates be found to be heterogeneous. The rejected model, i.e. the model not used as the primary model, will be checked in a sensitivity analysis. For example, if the fixed-effect model is used as the primary meta-analytical approach, the random-effects model will be checked in a sensitivity analysis, and vice versa. Results of combined analyses will be presented using a standard forest plot, reporting the country-specific overall crude and adjusted point estimates, and the pooled overall crude and adjusted point estimates, all with 95% CIs.

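### The pooled stillbirth ratio combines different gestational-age definitions (week 22 in three countries, week 28 in Sweden, none stated before July 2008), and no like-for-like estimate is planned beside it

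*Protocol*

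**What the plan says.** - **Outcome (Protocol 9.3.2.1).** The definition is "Stillbirth, as recorded in each country's birth registry". Low birth weight, preterm birth and low Apgar score in the same list have explicit cut-offs, and SGA and microcephaly have a 2-SD rule. Table 1 adds no gestational limit for stillbirth.
- **Registration (9.2).** Live births and stillbirths are recorded "in all countries except Sweden from gestational week 22 from July 2008 onwards; in Sweden, from gestational week 28 from July 2008 onwards".
- **Inclusion (9.2.1).** The cohort takes "All births from 1 January 2005 through 31 December 2015 (both dates inclusive) in Denmark, Finland, and Norway". For Sweden the window opens in July 2006 and closes at the end of 2016.
- **Denominator (9.2, repeated in substance in 9.7.1).** "Major congenital malformations and stillbirth prevalence will be described and compared using live and stillbirths as the denominator". The denominator therefore follows each register's threshold as well.
- **Pooling (9.7.7).** The similar healthcare systems and the "use of a common study protocol with well-defined selection of exposures, outcomes and covariates, a fixed-effects meta-analysis is justifiable applied". As a safeguard, "Homogeneity of the estimates will be verified, and a random-effects meta-analysis will be considered as an alternative should the estimates be found to be heterogeneous". Country-specific estimates are presented first and appear in the forest plot, and whichever of the two models is not chosen is run as a sensitivity analysis.
- **Limitations (9.9).** The difference in thresholds is not mentioned.

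**The concern.** As written, a fetal death at week 25 is a case in Denmark, Finland or Norway. In Sweden it enters neither the numerator nor the denominator. Sweden holds 500 of the 1,743 any-time exposed pregnancies in Table 3. The pooled ratio therefore averages an effect on death from week 22 with an effect on death from week 28, in proportions set by the country weights. It answers neither question exactly unless the effect is the same in both gestational periods, and the protocol neither states nor argues that. Stillbirth prevalences in the otherwise identical country tables also cannot be read against each other.

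For births before July 2008 the reader cannot tell which definition applies in any country. Stillbirth is a primary outcome in a safety study, so the meaning of its one combined estimate should be fixed before extraction.

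**Working it through.** **1. The plan's own figure.** Table 4 gives 2.373 as the upper limit for stillbirth against unexposed births. Inputs: p = 0.006, n1 = 1,743, n0 = 3,298,823 − 1,743 = 3,297,080, two-sided 95%, 80% probability, true ratio 1.0.

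SE = √[(1−p)/(n1·p) + (1−p)/(n0·p)] = √(0.09505 + 0.00005) = 0.3084

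Upper limit = exp[(1.960 + 0.842) × 0.3084] = 2.373, as stated. The figure is not in dispute. It applies one prevalence of 0.6% to all four countries, with no threshold attached.

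**2. Birth years with no stated threshold.** Denmark, Finland and Norway: January 2005 to June 2008 = 3.5 of 11 years (32%). Sweden: July 2006 to June 2008 = 2 of 10.5 years (19%).

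**3. Expected exposed stillbirths at 0.6%** (Table 3, any-time exposure):

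| Country | Exposed | Expected |
|---|---|---|
| Denmark | 388 | 2.3 |
| Finland | 388 | 2.3 |
| Norway | 467 | 2.8 |
| Sweden | 500 | 3.0 |

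All lie below the five-event limit in 9.7 for releasing registry data. Table 3 runs to 2016 and applies no exclusions, so these counts are if anything generous.

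**4. Assumption for the rest.** The protocol does not give the share f of stillbirths at weeks 22–27. Take f = 20% to 50% and read 0.6% as the prevalence from week 22. Sweden's recorded prevalence is then 0.6% × (1−f) = 0.48% to 0.30%, or 2.4 to 1.5 expected exposed events.

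**5. Precision as written.** Country weight = 1/[(1−p)/(a·p) + (1−p)/((N−a)·p)], with a exposed and N total births. This gives Denmark 2.34, Finland 2.34, Norway 2.82, and Sweden 2.41 (f = 20%) or 1.50 (f = 50%).

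- Sum 9.91 or 9.00; SE = 1/√sum = 0.318 or 0.333.
- Excludable upper limit 2.44 or 2.54.
- Sweden carries 24% or 17% of the weight.

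**6. Precision with week 28 or later everywhere.** Using the step 1 formula with p = 0.0048 or 0.0030:

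- Expected exposed events 1,743 × p = 8.4 or 5.2.
- SE = 0.345 or 0.437; upper limit 2.63 or 3.40.

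**7. Illustration of a gestation-dependent effect.** Suppose a true ratio of 2.0 at weeks 22–27 and 1.0 from week 28. The week-22 countries then estimate 1 + f = 1.20 to 1.50, and Sweden 1.00. Weights recomputed under these ratios are 9.01 (three countries) and 2.41 (Sweden) at f = 20%, and 11.28 and 1.50 at f = 50%.

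- f = 20%: exp[(9.01/11.42) × ln 1.20] = 1.155, which is 0.045 below 1.20.
- f = 50%: exp[(11.28/12.78) × ln 1.50] = 1.430, which is 0.070 below 1.50.

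**8. Can the homogeneity check see it?** For Sweden against the other three, SE of the difference in log ratios = √(1/9.01 + 1/2.41) = 0.725 at f = 20%, and √(1/11.28 + 1/1.50) = 0.868 at f = 50%. The differences are ln 1.20 = 0.182 and ln 1.50 = 0.405. Power at two-sided 5% is about 6% and 8%.

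**The case against.** **No bias within a country.** A reader might infer that the thresholds create a spurious association with gabapentin. They do not. Each country's ratio compares groups under one register rule, calendar year of delivery is in the propensity score (9.3.3), and only associations are pooled. This objection stands in full and limits the point to interpretation of the pooled ratio and comparability of prevalences.

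**The shift is small.** In the illustration the pooled ratio moves by 0.045 to 0.070, well inside random error when the excludable limit is about 2.4. This also stands. A definition can nevertheless be made clear whatever the precision.

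**Existing safeguards.** Country estimates, the forest plot and the random-effects alternative help a reader who knows the definitions differ. With 2 to 3 expected exposed events per country, the homogeneity check cannot be relied on to flag the difference. Extra analyses will not settle whether the effect varies by gestation either; they only make clear what each estimate refers to.

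**A week-28 outcome could hide harm.** If harm were confined to weeks 22–27, a week-28 ratio would be 1.0, while the registry-defined one would still show 1.155 to 1.430. It would also lose precision. This is a sound reason not to replace the registry-defined estimate.

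**The sentence in 9.2 may be a slip.** The same date is attached to both thresholds although the cohort starts earlier. It would be tempting to state as fact that Sweden registered only from week 28 to the end of 2016, but the text is too uncertain for that. Annex 3, to which 9.3.3 refers for operational definitions, is only a link in the copy at hand, so a harmonising rule there cannot be excluded.

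**Conclusion.** The point holds in limited form. Followed as written, the plan pools stillbirth from week 22 with stillbirth from week 28, leaves 32% (Sweden 19%) of the birth years without a stated threshold, and justifies fixed-effects pooling by a commonality this outcome lacks. Nothing in the plan provides a like-for-like estimate or warns the reader.

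The numerical effect is modest: none if the ratio is constant over gestation, and 0.045 to 0.070 below the week-22 value in a deliberately extreme scenario. Those figures rest on the assumed 20–50% share at weeks 22–27, on reading 0.6% as the week-22 prevalence, and on Table 3's counts.

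Two stronger readings are not supported. The documents do not show that the stillbirth ratio in any single country is distorted by the threshold. They also give no ground for claiming a material effect on the malformation ratio: the threshold touches its live-plus-stillbirth denominator, but at about 0.6% of births the effect is probably small.

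**What to change.** 1. In 9.2, confirm and correct the registration threshold for each country and calendar period over the whole study, including births before July 2008.
2. In 9.3.2.1 and 9.7.7, keep the registry-defined pooled estimate and prespecify beside it:
   - (a) a harmonised pooled estimate of stillbirth at 28 or more completed weeks, with the denominator restricted to births reaching 28 weeks, in all countries and years;
   - (b) an estimate from week 22, pooled only over the countries and periods that register from week 22.
3. In 9.7.7, do not rest fixed-effects pooling of stillbirth on a common outcome definition. In 9.9, list the threshold difference as a limitation.

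Cost: a gestational-age filter (Table 2 lists gestational age in all four birth registers) and one or two extra tables. Estimate (a) is less precise than the registry-defined one, with fewer expected exposed events and the wider limits shown in steps 5 and 6, and small-count suppression may restrict what individual countries can show.

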Study variable/role	Type of data	Data source(s)	Coding system(s) used
	Maternal morbidity (including indication for gabapentin) Markers of health care utilisation	Danish National Patient Registry, ³² Finnish Care Register for Health Care Finnish Register of Primary Health Care visits Norwegian Patient Registry ³⁷ Swedish National Patient Register ⁴³ Danish National Prescription Registry ³⁴ FinnishDatabase Finnish Prescription Register ³⁵ Norwegian Prescription Database ³⁵ Swedish Prescribed Drug Register ³⁵	ICD-10 for diagnoses, ATC for medication proxies
	Maternal medications	Danish National Prescription Registry ³⁴ Finnish Prescription Register ³⁵ Norwegian Prescription Database ³⁵ Swedish Prescribed Drug Register ³⁵	ATC
Loss to follow-up	Death, emigration [†]	Danish Civil Danish Civil Registration System ³⁰ Finnish Causes of Death Register Finnish Population Register Centre National Registry of Norway Swedish Cause of Death Register ⁴⁴ Swedish Total Population Register	A specific variable in each registry

*Data for the Medical Birth Register, the Register on Induced Abortions, the Malformation Register and the Prescription Register (3 months before last menstrual period) can be obtained from the Finnish Drugs and Pregnancy Project (DPP) database.

[†]Emigration data not available in the Norwegian dataset

[‡]Data available from 2008 onwards in Norway

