9.5. Study size

Table 3 shows estimated number of total pregnancies ending in live or stillbirth and pregnancies with AED exposure (any use, i.e., pregnancies exposed to monotherapy and pregnancies exposed to polytherapy).

Table 3. Estimated numbers of pregnancies ending in live or still birth (any use, i.e., pregnancies exposed to monotherapy and pregnancies exposed to polytherapy)*

	Denmark (2005-2016)	Finland (2005-2016)	Norway (2005-2016)	Sweden (2006-2016)	TOTAL
Live/still births	728,052	701,550	717,219 (657,451)	1,152,002	3,298,823

Table 3. Estimated numbers of pregnancies ending in live or still birth (any use, i.e., pregnancies exposed to monotherapy and pregnancies exposed to polytherapy)*

	Denmark (2005-2016)	Finland (2005-2016)	Norway (2005-2016)	Sweden (2006-2016)	TOTAL
Pregnancies with dispensation of Gabapentin, first trimester	374	374	344	500	1,592
Gabapentin, any time during pregnancy	388	388	467	500	1,743
Pregabalin, first trimester	372	1,020 (935)	248 (227)	1,230	2,870
Pregabalin, any time during pregnancy	377	1,053 (965)	225 (307)	1,275	2,930
Lamotrigine, first trimester	2,266	1,048 (961)	1,841 (1,688)	2,838	7,993
Lamotrigine, any time during pregnancy	2,379	1,104 (1,012)	2,110 (1,934)	2,991	8,584

*Number of exposed in Denmark and Sweden are the actual numbers for 2005-2016; estimated for Finland and Norway based on 2005-2015 data in parenthesis. No exclusion criteria are applied in this table.

The 2005-2016 estimated numbers of pregnancies ending in live or still birth for potentially analysis-relevant categories for Norway and Finland were unavailable at the time of writing the protocol but are estimated using data from 2005-2015 to provide the most conservative estimate.^{14,45,46,47}

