9.7.2. Calculation of incidence rates of postnatal outcomes

Incidence rate of each postnatal outcome will be computed as the number of first-recorded events during the follow-up divided by the total person-time at risk contributed by each livebirth. The follow-up for each newborn will begin on the date of birth and will end on the date of a given postnatal outcome, emigration, death, or the end of the observation period.

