exposure variable (yes/no), it is more likely that this misclassification would result in biasing towards the null than away from the null. Not all livebirths will have follow-up into the school age, and as postnatal neurodevelopmental disorders are diagnosed after the first year of age, primarily at school age, the number of events in gabapentin exposed pregnancies in the study period may not be sufficient to yield stable estimates of association, as specified in the provided feasibility counts in Table 3 and Annex 3. Emigration data (censoring variable) are not available in the Norwegian dataset, however, the impact of this is likely to be minimal. In 2019, 7,583 Norwegian citizens of all ages immigrated, 9,256 emigrated and the net immigration was -1673.⁶⁰ Children of school going age, born in the study period (1Jan2005 - 31Dec2015), who were exposed to gabapentin (or any of the other comparators) in utero, and who emigrated over the study period, are expected to be few; in Norway, gabapentin exposed pregnancies during the study period are approximately 467/657,451 (0.07%) of all pregnancies (Table 3). In addition, it is unlikely that the emigration pattern of gabapentin exposed paediatric subjects differs substantially from that of paediatric subjects in the other comparator groups.

The methods proposed to analyse data including propensity score stratification perform well when multiple outcomes are being examined.⁵² However, in case of model non-convergence, actions have been described in section 8.7.3.1 to achieve convergence. The study is performed in the Nordic countries where >90 % is of Caucasian ethnicity, and thus the available data on other ethnic groups are too limited to do stratified analyses, but the MAH has no reason to believe that the associations between gabapentin exposure and the studied outcome should be different in other ethnic groups or in other countries.

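### Section 9.2 says emigration data are unavailable for Sweden as well as Norway, but Table 2 and 9.9 except Norway only, so the Swedish censoring rule for the postnatal outcomes must be reconciled

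*Protocol*

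**What the plan says.** Five places in the protocol, and the abstract, bear on whether a child who leaves the country is censored:

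- **9.2 Setting.** Children are followed to the outcome, death, end of study, or "emigration (except Sweden and Norway, where emigration data are unavailable". This exempts both countries.
- **9.4, Table 2, loss-to-follow-up row (death, emigration).** The sources include the "Swedish Total Population Register". The footnote makes one exception: "Emigration data not available in the Norwegian dataset". The same row also lists the National Registry of Norway.
- **9.9 Limitations.** "Emigration data (censoring variable) are not available in the Norwegian dataset, however, the impact of this is likely to be minimal". Sweden is not mentioned.
- **9.7.2.** Follow-up "will end on the date of a given postnatal outcome, emigration, death, or the end of the observation period", with no exception for any country. The analysis description in the abstract reads the same way.
- **9.1.** Each country is said to have "routine and prospectively collected data on outpatient dispensings, live and still births, hospital diagnoses, migrations and deaths".

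Sections 9.6, 9.7 and 9.7.7 have each country run its own analysis. Only estimates go to the coordinating centre, which does not receive Swedish patient-level data.

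**The concern.** Section 9.2 is the only place that exempts Sweden, and it is an operative rule: it tells the analyst when a child stops being at risk. A Swedish analyst following 9.2 would not censor at emigration. One following 9.7.2 and the Table 2 footnote would. Because the countries work separately and send only estimates, the coordinating centre could neither see the choice nor reverse it.

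Without emigration censoring, a child who leaves Sweden keeps adding person-time until 31 December 2017 but can no longer have a diagnosis recorded there. Swedish incidence rates come out too low. Hazard ratios are distorted if emigration differs between the gabapentin and comparator groups. Sweden is the largest contributor in Table 3 and has the longest stated follow-up. If the Swedish data really are unavailable, the error lies elsewhere: the Table 2 footnote is incomplete, and 9.9 discloses the limitation for one country instead of two.

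**Working it through.** **Inputs from the protocol (Table 3 in 9.5; dates in 9.2)**

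- Live/still births: Denmark 728,052; Finland 701,550; Norway 717,219; Sweden 1,152,002.
- "Gabapentin, any time during pregnancy": Denmark 388; Finland 388; Norway 467; Sweden 500.
- Swedish births from 1 July 2006 to 31 December 2016, followed to 31 December 2017.

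**The plan's own figures**

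- 728,052 + 701,550 + 717,219 + 1,152,002 = 3,298,823, as stated.
- 388 + 388 + 467 + 500 = 1,743, as stated.
- Norwegian exposed share in 9.9: 467/657,451 = 0.07%, as stated.
- Swedish follow-up by these dates runs from 1 to 11.5 years, matching the maximum in 9.2.

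**Share affected under each version**

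- Sweden alone: 1,152,002/3,298,823 = 34.9% of births; 500/1,743 = 28.7% of gabapentin-exposed pregnancies.
- Norway only without emigration censoring (Table 2, 9.9): 467/1,743 = 26.8% of exposed.
- Sweden and Norway without it (9.2): (500 + 467)/1,743 = 967/1,743 = 55.5% of exposed.

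These shares are approximate. Table 3 applies no exclusions, is headed 2005-2016 for three countries whose births are included only through 2015, and predates the removal of Norwegian births before 2008 from the postnatal analysis.

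**Size of the effect on Swedish person-time**

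The protocol gives no Swedish emigration rate, so a range is assumed: a constant rate r of 0.1% to 1% per year. Births are taken as uniform over the period, so potential follow-up T is uniform on 1 to 11.5 years, with mean (1 + 11.5)/2 = 6.25 years.

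- Person-time counted without censoring: 6.25 years per child.
- Person-time truly observable: the mean over T of (1 − exp(−rT))/r.
- Inflation: 6.25 divided by the observable person-time, minus 1.

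| Assumed r per year | Observable years per child | Inflation of person-time | Rate too low by |
|---|---|---|---|
| 0.1% | 6.226 | 0.4% | 0.4% |
| 0.2% | 6.202 | 0.8% | 0.8% |
| 0.5% | 6.131 | 1.9% | 1.9% |
| 1% | 6.016 | 3.9% | 3.75% |

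**Effect on a ratio**

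If r is the same in both groups, the understatement cancels in the Swedish rate ratio. If r were 0.2% in the exposed and 1% in the comparators, the ratio would be multiplied by 6.202/6.016 = 1.031. With the rates reversed, it would be multiplied by 0.970. A fivefold difference in emigration therefore moves the Swedish ratio by about 3%.

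**The case against.** A reader might infer that Table 2 proves Swedish emigration dates are in hand, so that 9.2 simply throws away an available variable. The documents do not support that. The same row lists the National Registry of Norway, and its footnote says the Norwegian dataset has no emigration data. Being listed in that row therefore does not show that the extract holds the dates. The statement on migrations in 9.1 covers Norway too and has the same weakness. No passage says in words that Swedish emigration data are available, and 9.2, the only explicit statement about Sweden, says they are not. This objection stands. What survives it is that the footnote and 9.9 single out Norway, which cannot be squared with 9.2.

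The second objection is that little is at stake. Postnatal outcomes are secondary, and the protocol warns that events may be too few for stable estimates. The missing censoring applies to every exposure group. If Sweden's weight in the pooled estimate equalled its share of exposed pregnancies, the 3.1% shift above would become about 0.287 × 3.1% = 0.9%. Table 4 puts the upper limits that can be ruled out against the unexposed at 2.373 (0.6% prevalence, including ASD) and 1.950 (1% prevalence, including ADHD). This also largely stands, and it limits the weight of the point.

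Third, 9.9 closes by arguing that exposed and comparator children are unlikely to differ in emigration. That reasoning is not specific to Norway and would carry over to Sweden. The migration and exposure figures offered with it, however, are Norwegian only.

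**Conclusion.** The contradiction is real and sits in a rule that determines the analysis: 9.2 exempts Sweden and Norway, the Table 2 footnote and 9.9 except Norway only, and 9.7.2 and the abstract except no one. The documents cannot show which statement about Sweden is correct, only that one set must change.

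The effect is confined to the secondary postnatal outcomes. A reader might infer material bias from Sweden's 34.9% of births, but that share measures Sweden's size, not the size of an error. The inflation of Swedish person-time is about 0.4% to 3.9%, resting on the assumed 0.1% to 1% emigration per year and uniform births. It bears mainly on absolute rates, and hazard ratios change materially only if emigration differs by exposure group. The primary malformation and birth-outcome analyses do not use this censoring rule. If 9.2 proves right, the main consequence is a limitation disclosed for 26.8% of exposed pregnancies when it would apply to 55.5%, subject to the Table 3 caveats above.

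**What to change.** Before Swedish data are extracted, confirm with the Swedish data custodian whether emigration dates can be obtained from the Total Population Register already listed in Table 2.

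- **If they can:** remove Sweden from the exception in 9.2 and censor Swedish children at emigration.
- **If they cannot:** add Sweden to the Table 2 footnote, state the country exception in 9.7.2, and extend 9.9 to Sweden, giving the combined 967 of 1,743 exposed pregnancies and an impact argument that covers both countries.

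In either case, 9.7.2 and the abstract should carry the Norwegian exception that 9.2, Table 2 and 9.9 already agree on.

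The cost is a wording change and at most one variable from a register already named as a source. No planned sample-size or precision figure changes.
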